This project will contribute toward determining whether these potentially beneficial properties of nebivolol, known to improve diastolic dysfunction, will also improve PH severity in patients with HFpEF. This contribution will be important because it could uncover a potential treatment for a disease category that currently has no accepted treatments. If nebivolol significantly improves PH severity in patients with HFpEF, it can be further researched as a probable treatment. Furthermore, this project should also advance knowledge of the hemodynamic effects of chronic nebivolol treatment in HFpEF patients, as very few clinical studies have measured hemodynamics by right heart catheterization both before and after chronic oral treatment.

Methods

This project will be a prospective, open-label four-month clinical pilot study of 40 patients with PH and HFpEF. Patients will be started at 2.5 mg of nebivolol by mouth daily if they were not taking a beta-blocker at enrollment, and titrated up to 10 mg daily, as tolerated. Patients who cannot tolerate a dose increase will continue on the maximum tolerated dose throughout the study. Patients already on a beta-blocker at enrollment will begin on 5 mg and will be titrated to 10 mg daily. DNA and RNA will be collected for genomic studies of disease and drug response. All study procedures will occur at either the UF Clinical Research Center (CRC) or Shands Hospital.

Test/Procedure	Visit 1/1A (wk 0-1)	Call 1 (wk 1)	Call 2 (wk 2)	Visit 2 (wk 4)	Call 3 (wk 5)	Visit 3 (wk 8)	Call 4 (wk 9)	Visit 4 (wk 18)
right heart catheterization	X*							X
transthoracic echo	X*							X
electrocardiogram	X			X		X		X
6-minute walk distance	X			X		X		X
vital signs	X			X		X		X
dyspnea index	X			X		X		X
complete blood count	X			X		X		X
INR	X					X		X
liver function test	X			X		X		X
basic metabolic panel	X			X		X		X
nt-proBNP	X					X		X
RNA collection	X			X		X		X
DNA collection				X		X		
serum collection	X			X		X		X
change in nebivolol dose	X		X	X				X
adverse effect assessment		X	X		X		X	
medication history	X			X		X		X

* = if not done within previous 3 months as part of clinical care

Visit 1 (week 0):

- Blood sample: 2x 8 mL PAXgene (RNA), 1x 10mL lavender top (plasma and PBMCs), 1x 3mL lavender top (CBC with diff), 2x 4mL Li Heparin (nt-proBNP, CMP), 1x2.7mL blue top (INR)
- Vital signs: blood pressure, pulse, respirations, height, weight, etc.
- Dyspnea index
- 6-minute walk test
- Medication history
- EKG

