- Patients will be asked to take oral nebivolol 2.5 mg (or 5 mg) once daily until Visit 2 (**if visit 1A is not needed**). Instruct patient to discontinue previous beta-blocker and begin nebivolol today if they have not taken any beta-blocker today, and tomorrow if they have already taken a beta-blocker today.
- Place note in medical record documenting name of study, responsible physician, procedures, and medication dose.
- If possible, schedule Visit 1A or Visit 2.
- Once complete, provide patient with compensation (\$50).

Visit 1A – IF NEEDED (week 0-1):

- If the patient has not received a two-dimensional transthoracic echocardiogram (TTE) within 3 months of enrollment, it will be done for research purposes, possibly on the same day as visit 1.
- If the patient has not received a right heart catheterization (RHC) within 3 months of enrollment, it will be done for research purposes (Appendix 1).
- Patients will be asked to take oral nebivolol 2.5 mg (or 5 mg) once daily until Visit 2. Instruct patient to discontinue previous beta-blocker and begin nebivolol today if they have not taken any beta-blocker today, and tomorrow if they have already taken a beta-blocker today.
- Once complete, provide patient with compensation (\$200).

Phone Call 1 (week 1):

- How does patient feel compared to before starting study drug?
- Any perceived side effects?
- If not done already, schedule Phone Call 2

Phone Call 2 – IF NEEDED (week 2):

- How does patient feel compared to before starting study drug?
- Any perceived side effects?
- If tolerated, increase nebivolol dose to 5 mg (after approval by study physician)
- If not done already, schedule Visit 2.

Visit 2 (week 4):

- Blood sample: 1x 6 mL purple top (DNA), 1x 8 mL PAXgene (RNA), 1x 10mL lavender top (plasma and PBMCs), 1x 3mL lavender top (CBC with diff), 1x 4mL Li Heparin (CMP)
- Vital signs: blood pressure, pulse, respirations, height, weight, etc.
- Dyspnea index
- 6-minute walk test
- Medication history
- EKG
- If tolerated, increase nebivolol dose to 10 mg once daily.
- Update medical record to reflect new dose.
- If possible, schedule Visit 3.
- Once complete, provide patient with compensation (\$40).

Phone Call 3 (week 5):

- How does patient feel compared to before starting study drug?
- Any perceived side effects?
- Provide results of safety assessment (everything looks similar to baseline OR significant difference in _____; the study physician recommends you _____.)

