To assure any effect on hemodynamics are not due to other medications, patients must have no changes within one month to their cardiovascular medication regimen, including ACE-inhibitors, angiotensin receptor blockers, diuretics, and nitrates. Exclusion criteria include:

1. Other causes of heart failure other than diastolic dysfunction, such as restrictive cardiomyopathy or infiltrative cardiomyopathy
2. Women who are pregnant or nursing
3. Liver cirrhosis,
4. primary valvular disease
5. Acute coronary syndrome
6. Causes of PH other than that of heart failure, such as: chronic thromboembolic PH, sickle-cell disease, or sarcoidosis
7. Severe bradycardia or greater than 1st degree heart block
8. Decompensated heart failure
9. Current use of a third generation beta-blocker (nebivolol, carvedilol, or labetalol) or high dose of other beta-blockers (greater than 100 mg daily of metoprolol, or equivalent).

Plans for subject selection, recruitment, and documentation of informed consent

This study will include PH patients from Shands Hospital and UF Health pulmonary hypertension and cardiology clinics. Eligibility will be reviewed and if requirements are met, patients will be approached to gauge interest. If interested, patients will be asked to provide informed written consent.

Description of Procedures

Hemodynamic Measurements. To confirm the diagnosis of PH associated with HFpEF and obtain baseline hemodynamic measurements, right heart catheterizations (RHCs) will be performed by UF cardiologists and pulmonologists using standard techniques. Any procedures done during catheterization beyond those mentioned will be at the discretion of the physician performing the for clinical indications.

Transthoracic echocardiograms (TTEs) performed by UF Health technicians will also be used to obtain further hemodynamic parameters, including those that are indicative of diastolic dysfunction. TTEs will be read by a cardiologist as per American Society of Echocardiography guidelines. Diastolic dysfunction will be determined by tissue Doppler imaging. RV measurements including size, lateral tricuspid annular velocity, E wave, A wave, and isovolumic relaxation time will be performed.

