Functional Assessments. The 6-minute walk test will be performed in accordance with standard practice both at baseline and at completion of the study. Briefly, subjects will be asked to walk for six minutes along a pre-measured path, with a practice walk being performed first. Distance walked, oxygen saturation, and a Dyspnea Index will be determined.

Statistical Methods

Planned statistical analysis: Student's t-test for paired samples will be used to determine differences between hemodynamic measurements taken before and after six months of nebivolol
Personalized Treatment of PH with DD Protocol, Version 3, 10/08/18

treatment. Thus, each patient will serve as their own control. The two primary efficacy phenotypes to be measured are mPAP and PCWP. In secondary analyses, mitral valve Doppler flow velocity pattern, CO, PVR, CI and TPR will also be analyzed in an attempt to better characterize the mechanisms by which nebivolol affects the hemodynamic profile. In addition, Student's t-test for paired samples will be used to determine differences in 6-minute walk time before and after nebivolol treatment. Fisher's Exact Test will be used to compare dyspnea scores before and after six months of nebivolol treatment. In all analyses, $P \leq 0.05$ in a two-tailed distribution will be considered statistically significant. Statistical analyses will be performed using SAS 9.2 (SAS Institute, Cary, NC).

Rationale for selection of subject

Sample Size Calculation. Change in mean pulmonary artery pressure was used to estimate the sample size required to achieve satisfactory statistical power for this study. We calculated our sample size to be well-powered to detect a 15% decrease in mean mPAP (a clinically significant change). This would be approximately 4 mmHg at our minimum mPAP cut-off of 25 mmHg. We assumed a standard deviation of 5.5 derived from previous HFpEF treatment studies.¹³ Thus, with a power of 0.95, and a two-sided α of 0.05, we would require a sample size of 27 patients. Because of the length of the study, we estimate an additional 30% will be needed to offset study attrition, thus a total sample size up to 40 patients will be enrolled.

Safety Monitoring and Assessment

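### The baseline catheterization may be up to 3 months old but drug stability is required only for one undated month, so an earlier drug change can be counted as a nebivolol effect

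*Combined protocol and SAP*

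**What the plan says.** **Stability rule.** Eligibility Criteria: "patients must have no changes within one month to their cardiovascular medication regimen, including ACE-inhibitors, angiotensin receptor blockers, diuretics, and nitrates". The purpose is given in the same sentence: "To assure any effect on hemodynamics are not due to other medications". The sentence does not say one month before what.

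**Baseline RHC.** Description of Procedures (Hemodynamic Measurements) says that, to confirm the diagnosis and "obtain baseline hemodynamic measurements, right heart catheterizations (RHCs) will be performed". The footnote to the schedule table limits the Visit 1/1A RHC and echocardiogram to cases "if not done within previous 3 months as part of clinical care". Visit 1A is consistent with this. A research RHC is done "If the patient has not received a right heart catheterization (RHC) within 3 months of enrollment", and a research echocardiogram "If the patient has not received a two-dimensional transthoracic echocardiogram (TTE) within 3 months of enrollment". A recent clinical RHC is therefore the before-treatment value. If no Visit 1A is needed, nebivolol starts at Visit 1 or the next day.

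**Analysis.** Statistical Methods: "The two primary efficacy phenotypes to be measured are mPAP and PCWP". Both are compared before and after treatment by a paired t-test. "Thus, each patient will serve as their own control". The study is open-label and no comparison arm is described. Medication history is taken at Visits 1 to 4, but Statistical Methods makes no use of it.

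**The concern.** The two windows do not meet. A patient can have a clinical RHC, then a change of diuretic, nitrate or other cardiovascular drug, then one stable month, and still enroll with the pre-change RHC as baseline. The protocol has then been followed exactly, yet the paired difference contains the effect of the other drug as well as that of nebivolol.

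With each patient as their own control, nothing in the planned analysis can separate the two effects, and both primary endpoints are affected. The stability rule exists to prevent this, so as written it does not secure its own purpose. The 3-month echocardiogram window raises the same issue only for the secondary Doppler measures.

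**Working it through.** **1. The plan's own figure.** Inputs from Sample Size Calculation: fall in mPAP 4 mmHg, SD 5.5 (taken here as the SD of the paired change), power 0.95, two-sided alpha 0.05. The noncentrality is 4 × √27 / 5.5 = 3.78 with 26 degrees of freedom. Exact paired t-test power is 95.3%, and 27 is the smallest n that reaches 95%. The stated sample size reproduces and is not in question.

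**2. The uncovered interval.** One month = 4.35 weeks; 3 months = 13.04 weeks. Visit 1A falls in week 0-1. If it is needed only for the echocardiogram, a patient with an older clinical RHC may start nebivolol one week after enrollment.

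| Month counted | Start at enrollment | Start one week later |
|---|---|---|
| back from enrollment | 13.04 − 4.35 = 8.7 weeks | 8.7 + 1 = 9.7 weeks |
| back from nebivolol start | 13.04 − 4.35 = 8.7 weeks | 14.04 − 4.35 = 9.7 weeks |
| either side of the RHC | 13.04 − 4.35 = 8.7 weeks | 14.04 − 4.35 = 9.7 weeks |
| back from the RHC | all 13.0 weeks | all 14.0 weeks |

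These are maxima, and no reading brings the gap to zero. On the first two readings, exposure is mainly in patients whose clinical RHC is more than about one month old. Patients catheterized at Visit 1A have no such gap. If RHC age were uniform over the 3 months (an assumption), two thirds of patients with a clinical RHC would be exposed, with a mean gap of 4.35 weeks.

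**3. Possible effect on the mPAP test.** Let f be the share of analysed patients with a drug change that lowers mPAP by D mmHg. Neither f nor D is in the documents; the values below are assumptions. With no nebivolol effect, the mean change is shifted by f × D and the SD of change becomes √(5.5² + f(1 − f)D²). The noncentral t at n=27, two-sided 0.05, gives:

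| f | D (mmHg) | Bias (mmHg) | SD | Noncentrality | False positives |
|---|---|---|---|---|---|
| 0 | – | 0 | 5.50 | 0 | 5.0% |
| 0.10 | 2 | 0.20 | 5.53 | 0.19 | 5.4% |
| 0.15 | 3 | 0.45 | 5.60 | 0.42 | 6.9% |
| 0.30 | 3 | 0.90 | 5.67 | 0.82 | 12.5% |

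Against the 4 mmHg target, 0.45 is 11% and 0.90 is 23%. The last row is a high case. It needs a pressure-lowering change in 0.30/0.50 = 60% of exposed patients if half of all patients are exposed, or 0.30/0.667 = 45% if two thirds are.

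**4. PCWP.** The documents give no SD. For an assumed SD of 4 to 7 mmHg and D=3, the same calculation gives 8.5% to 6.2% (f=0.15) and 18.7% to 9.7% (f=0.30).

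**5. The opposite direction.** If the changes instead raise mPAP by 3 mmHg and nebivolol truly lowers it by 4, the mean fall is 4 − 3f. Power drops from 95% to 89% (f=0.15) or 78% (f=0.30).

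**The case against.** **The effect may be small.** This stands in part. The lower two cases move mPAP by 0.2 to 0.45 mmHg and barely raise the error rate. The false-positive cases also assume that every change lowers pressure; mixed changes would partly cancel. For an uncontrolled pilot of up to 40 patients this keeps the point moderate. It does not remove it, because the true f and D are unknown and the planned analysis would not reveal them.

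**Enrollment is the natural reference date.** This is fair, since the sentence sits among the eligibility criteria. Counting back from the RHC is strained, so the 13 to 14 week figure should not be used as the headline. The enrollment reading still leaves up to 8.7 or 9.7 weeks open.

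**The data forms may already capture drug changes.** The patient and RHC data collection forms and Appendix 1 are not in the text available, so this cannot be judged. Recording the changes would still not put them into the analysis.

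**Changes after nebivolol start.** No section requires other cardiovascular drugs to stay unchanged during the 18 weeks. A reader might fold this into the same point. It is a separate exposure, and it needs separate handling because such changes may be responses to nebivolol.

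**Conclusion.** The point holds and should be fixed. A cardiovascular drug change between the baseline RHC and nebivolol start is allowed within an uncovered interval of up to about 8.7 weeks, or 9.7 with an echo-only Visit 1A in week 1. Its effect would be attributed to nebivolol on both primary endpoints. That follows from the text alone.

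The consequence is much less certain. The error rates of 5.4% to 6.9%, and 12.5% in the high case, rest on assumed f and D, n=27, SD 5.5, no nebivolol effect and uniformly pressure-lowering changes.

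A reader might infer that the primary result will be biased in favour of nebivolol, or that most patients will have an outdated baseline. The documents support neither. They do not say how many patients will rely on an older clinical RHC, how many will have had a drug change, or in which direction. Treatment reductions would work against nebivolol.

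**What to change.** 1. State the date from which the one month is counted, and reconcile that date with the 3-month baseline RHC window.
2. From the medication history already taken at Visit 1, record any cardiovascular drug change since the baseline RHC, if the data forms do not already do so.
3. Prespecify a supportive paired analysis of mPAP and PCWP that excludes patients with a cardiovascular drug change between the baseline RHC and nebivolol start, other than the planned beta-blocker switch. Report how many were excluded.
4. Report separately the number with a change after nebivolol start. Treat any analysis that excludes them as a further sensitivity analysis, because it can introduce selection.

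The primary test and the planned n of 27 stay as they are, and no repeat catheterization is proposed.

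**Cost.** One clarified sentence, possibly one data item, and one supportive analysis on a smaller sample. The number excluded cannot be derived from the documents. As examples, with SD 5.5, a fall of 4 mmHg and CI half-width t × 5.5/√n:

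| n | Power | 95% CI half-width (mmHg) |
|---|---|---|
| 27 | 95% | 2.2 |
| 24 (3 excluded) | 93% | 2.3 |
| 22 (5 excluded) | 90% | 2.4 |

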PROTOCOL

Title: Improving treatment personalization of pulmonary hypertension associated with diastolic heart failure

Protocol Version: 3
10/08/2018

Investigators:

[name], PhD, Assistant Professor
Department of Pharmacotherapy and Translational Research, UF

[name], Associate Professor
Division of Pulmonary, Critical Care and Sleep Medicine, UF

[name], Assistant Professor
Division of Pulmonary, Critical Care and Sleep Medicine, UF

Study Hypothesis and Specific Aims

The objective of this application is to evaluate nebivolol as a potential treatment for patients with pulmonary hypertension (PH) associated with diastolic heart failure, or heart failure with preserved ejection fraction (HFpEF). Our central hypothesis is that nebivolol improves PH severity in patients with HFpEF, as measured by hemodynamic and clinical parameters. The rationale for this research is that once we determine the extent to which nebivolol improves PH, it could be developed as a treatment for PH and HFpEF, especially if patients who respond best can be identified before treatment.

We will test our central hypothesis and accomplish these objectives by pursuing the following specific aim:

Define the clinical role of nebivolol as a potential treatment for PH associated with HFpEF using hemodynamic and functional status measurements.

Our working hypothesis is that nebivolol, via its β_1 -antagonistic and β_3 -agonistic activities, as well as its anti-inflammatory, anti-proliferative, and endothelial NO-stimulating properties, will decrease pulmonary pressures and improve 6-minute walk distance and dyspnea scores in patients with HFpEF-associated PH.

Background and Significance

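### Two primary endpoints, mPAP and PCWP, are each tested at two-sided 0.05, and no rule says how the two results are read together

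*Combined protocol and SAP*

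**What the plan says.** Four parts of the protocol bear on this point.

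- **Statistical Methods, planned analysis.** "The two primary efficacy phenotypes to be measured are mPAP and PCWP". Neither is ranked above the other. The test is the same for both: "Student's t-test for paired samples will be used to determine differences between hemodynamic measurements", with each patient as his or her own control. One sentence sets the threshold for all analyses: P ≤ 0.05 "in a two-tailed distribution will be considered statistically significant".
- **Sample Size Calculation.** "Change in mean pulmonary artery pressure was used to estimate the sample size required", and no effect size or standard deviation is given for PCWP. The result is stated as: "Thus, with a power of 0.95, and a two-sided α of 0.05, we would require a sample size of 27 patients".
- **Study Hypothesis and Specific Aims.** "Our central hypothesis is that nebivolol improves PH severity in patients with HFpEF, as measured by hemodynamic and clinical parameters". The working hypothesis that follows predicts lower pulmonary pressures together with better walk distance and dyspnea scores. Neither statement says what is concluded if one primary endpoint succeeds and the other does not.
- **Methods.** "This project will be a prospective, open-label four-month clinical pilot study of 40 patients with PH and HFpEF".

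I found no testing order, alpha split or both-required rule in any section, and no statement that one endpoint is enough.

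**The concern.** Three success rules fit the present text: either endpoint suffices, both are needed, or mPAP leads. They agree when the two results agree and can differ when one primary is significant and the other is not. Under the first rule the two full-level tests give two chances of a false positive, so the error across the pair exceeds 5%. Under the second it does not.

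Because no rule is chosen, the choice could be made once the results are known. The consequence is limited but real: the background section says that a significant improvement in PH severity would justify further research on nebivolol as a probable treatment, and the plan does not define that outcome across its two primary endpoints.

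**Working it through.** **Inputs from the plan.** Two primary endpoints; paired t-test; two-sided 0.05 for each; mPAP decrease of 4 mmHg (15% of 25 mmHg, rounded up from 3.75); SD 5.5 mmHg, which reproduces the plan's figure when taken as the SD of the paired change; power 0.95; n = 27; 30% attrition; up to 40 enrolled.

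**Assumed, because the documents do not give them.** The correlation between the changes in mPAP and PCWP, taken as non-negative and shown as a range; and a smaller true mPAP decrease of 3 mmHg, used only to price the fix.

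**1. The plan's own figure.** With the noncentral t distribution and noncentrality (4/5.5)·√n, power is 0.945 at n = 26 and 0.953 at n = 27, so 27 is the smallest n that reaches 0.95. Attrition: 27/0.7 = 38.6, which rounds up to 39 and is consistent with up to 40. The sample size is correct for a 4 mmHg decrease and is not part of this point.

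**2. Either endpoint counts, both nulls true.** If the tests are independent, the error is 1 − 0.95² = 0.0975. If they are correlated, P(at least one significant) = 0.05 + 0.05 − P(both significant), from the bivariate normal at |z| > 1.96. For a false improvement, the corresponding formula is 0.025 + 0.025 − P(both z < −1.96).

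| Assumed correlation | At least one false significant result (reference 5%) | At least one false improvement (reference 2.5%) |
|---|---|---|
| 0 | 9.75% | 4.9% |
| 0.5 | 9.1% | 4.5% |
| 0.7 | 8.3% | 4.2% |
| 0.8 | 7.8% | 3.9% |
| 0.9 | 7.0% | 3.5% |

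Example at 0.7: P(both < −1.96) = 0.0083. The false-improvement figure is 0.05 − 0.0083 = 0.0417. The two-sided figure is 0.10 − 2 × 0.0083 = 0.0834, or 0.0835 before rounding. Simulated paired t-tests at n = 27 (1,000,000 replicates) give 9.2%, 8.4%, 7.9% and 7.1% at correlations 0.5, 0.7, 0.8 and 0.9, so the normal approximation is adequate.

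**3. Both endpoints required.** A false joint claim needs every true null to be rejected at 0.05, so its probability cannot exceed 0.05. Power under this rule cannot be computed, because the plan gives no PCWP effect or SD.

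**4. Fixed order, mPAP then PCWP.** If the mPAP null is true, any false claim must begin with a false rejection for mPAP, so the error is at most 0.05. If mPAP truly changes and PCWP does not, the only possible false claim is for PCWP, again at most 0.05. Requiring a significant *decrease* in mPAP before PCWP is tested only makes the second step harder to reach. mPAP is still tested at the full 0.05, so its power at n = 27 stays at 0.953.

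**5. Price of the fixed order: the chance that mPAP is not significant (1 − power).**

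| True mPAP decrease, SD 5.5 | n = 27 | n = 28 (40 × 0.7) |
|---|---|---|
| 4 mmHg | 4.7% | 4.0% |
| 3.75 mmHg (exactly 15% of 25) | 7.4% | 6.5% |
| 3 mmHg (assumed) | 22% | 21% |

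**The case against.** **The inflation is conditional.** It arises only if one endpoint alone counts as success, and the protocol never says that it does. The working hypothesis is worded jointly, covering pulmonary pressures in the plural together with functional measures, which leans towards needing more than one result. This stands as a limit on the finding. It does not remove it, because a prediction about several outcomes is not a rule for deciding from two P values.

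**mPAP may already be the lead endpoint, because the sample size rests on it.** That is a reasonable guess at intent. But basing a sample size on one endpoint does not order the tests, and the plan calls both endpoints primary.

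**The independence figure overstates the problem.** This stands. The background section attributes raised pulmonary artery pressure in these patients to backward transmission of raised left atrial pressure, so positively correlated changes are to be expected. 9.75% is therefore an upper bound for non-negative correlation and not a central estimate.

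**It is a pilot, and the stated consequence is further research.** This stands as to severity. Even so, the study names primary efficacy endpoints, sets a significance threshold and plans for 0.95 power, so it is fair to ask how its primary results will be read.

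A reader might infer that the trial's false-positive rate is 9.75%, or that the investigators intend to choose the better endpoint afterwards. The documents support neither. The first needs both an either-endpoint rule and independence; the second is a possibility left open, not something the plan provides for.

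**Conclusion.** The point holds in a limited form. The plan names two primary endpoints, applies the full two-sided 0.05 to each, and has no rule for combining them. On an either-endpoint reading the error across the two primaries is about 7% to 8.3% at assumed correlations of 0.7 to 0.9, and for false improvement about 3.5% to 4.2% against 2.5%. On a both-required reading nothing is inflated. The correlations are assumptions, and the figures describe only these two tests.

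This should be corrected because the remedy is cheap and the ambiguity is easy to remove, not because the excess is large. The calculation says nothing about other sources of error in an uncontrolled, open-label before-after comparison, and the remedy does not reduce them.

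**What to change.** Make both changes to Statistical Methods before outcome data are analysed.

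1. Amend the sentence that sets P ≤ 0.05 for all analyses so that it excepts the primary endpoints. If it is left as it stands, it would still call PCWP significant when mPAP fails, and so contradict the new rule.
2. Add: *mPAP will be tested first at two-sided 0.05; PCWP will be tested at two-sided 0.05 as a primary endpoint only if mPAP shows a significant decrease, and otherwise will be reported descriptively with its confidence interval.* Specifying a decrease matters, since a significant worsening of mPAP should not open the PCWP test.

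The order is the investigators' choice; mPAP first fits because the sample size is built on it. A both-required rule or Holm's procedure would also be valid. Under Holm, mPAP power at n = 27 would lie between 0.912 (tested at 0.025) and 0.953.

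**Cost.** Two sentences of text; no added patients, visits or data, and no loss of mPAP power. The downside is that PCWP cannot be declared a significant primary result when mPAP fails. The second table in the working gives the chance of that, which becomes material if the true mPAP effect is well below the planned 4 mmHg.

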- If not done already, schedule Visit 3.

Visit 3 (week 8):

- Blood sample: 1x 6 mL purple top (DNA), 1x 8 mL PAXgene (RNA), 1x 10mL lavender top (plasma and PBMCs), 1x 3mL lavender top (CBC with diff), 2x 4mL Li Heparin (nt-proBNP, CMP), 1x2.7mL blue top (INR)
- Vital signs: blood pressure, pulse, respirations, height, weight, etc.
- Dyspnea index
- Medication history
- 6-minute walk test
- EKG
- If possible, schedule Visit 4.
- Once complete, provide patient with compensation (\$40).

Phone Call 4 (week 9):

- How does patient feel compared to before starting study drug?
- Any perceived side effects?
- Provide results of safety assessment (everything looks similar to baseline OR significant difference in _____; the study physician recommends you _____.)
- If not done already, schedule Visit 4.

Visit 4 (week 18):

- Blood sample: 2x 8 mL PAXgene (RNA), 1x 10mL lavender top (plasma and PBMCs), 1x 3mL lavender top (CBC with diff), 2x 4mL Li Heparin (nt-proBNP, CMP), 1x2.7mL blue top (INR)
- Vital signs: blood pressure, pulse, respirations, height, weight, etc.
- Dyspnea index
- Medication history
- 6-minute walk test
- EKG
- Two-dimensional transthoracic echocardiogram (TTE) for research purposes
- RHC for research purposes (Appendix 1).
- Based on study physician recommendation, patients will be advised on how to proceed with beta-blocker treatment after the end of the study.
- Update medical records to indicate patient has completed study.
- Once complete, provide patient with final compensation (\$250).

Eligibility Criteria

Study Population. This study will include PH patients from Shands Hospital and UF Health pulmonary hypertension and cardiology clinics. Patients must be diagnosed with PH by right heart catheterization (RHC). This procedure is the gold-standard for PH diagnosis and is the most accurate way to measure the hemodynamics necessary to differentiate subtypes of PH. Inclusion criteria for this study include:

1. Adults (≥ 18 years of age) with World Health Organization Group 2 Pulmonary Hypertension:
 - a. Mean pulmonary artery pressure (mPAP) ≥ 25 mmHg,
 - b. And pulmonary capillary wedge pressure (PCWP) ≥ 15 mmHg or left ventricular end diastolic pressure (LVEDP) ≥ 15 mmHg

2. Evidence of either diastolic dysfunction on echocardiogram OR elevated filling pressures on invasive hemodynamic testing OR BNP>200 (NT-proBNP>220) pg/mL
3. NYHA class II-IV symptoms
4. Left ventricular ejection fraction (LVEF) \geq 45%

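### Dyspnea scores taken from the same patients before and after nebivolol are to be compared with Fisher's Exact Test, which assumes independent groups and is not a test of within-patient change.

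*Combined protocol and SAP*

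**What the plan says.** All of the relevant text is in the combined protocol and SAP.

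- **Statistical Methods, planned statistical analysis.** On dyspnea: "Fisher's Exact Test will be used to compare dyspnea scores before and after six months of nebivolol treatment". Paired t-tests are named for the hemodynamic measurements and for the walk test ("paired samples will be used to determine differences in 6-minute walk time before and after nebivolol treatment"). The paragraph also says that "each patient will serve as their own control". That remark follows the hemodynamic sentence, so extending it to dyspnea is an inference. Two-sided P of 0.05 or less is the threshold for every analysis.
- **Methods.** The design is a "prospective, open-label four-month clinical pilot study of 40 patients with PH and HFpEF", with no comparison group. The schedule has the dyspnea index at Visits 1, 2, 3 and 4, the last at week 18.
- **Functional Assessments.** "Distance walked, oxygen saturation, and a Dyspnea Index will be determined". No section names the instrument or gives its range or a cut-point.
- **Study Hypothesis and Specific Aims.** The working hypothesis is that nebivolol "will decrease pulmonary pressures and improve 6-minute walk distance and dyspnea scores in patients with HFpEF-associated PH".
- **Status of the endpoint.** "The two primary efficacy phenotypes to be measured are mPAP and PCWP", so dyspnea is not primary.

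**The concern.** Each patient contributes one score before treatment and one after, so the two sets of scores are dependent by design. Fisher's Exact Test can be applied to them in two ways, and neither suits the question.

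1. **Time-by-score table.** This treats n patients as 2n unrelated observations. It discards the pairing and, if the score has more than two levels, its ordering.
2. **Before-by-after cross-table.** Each patient is counted once, but the null hypothesis is that the two scores are unassociated. Patients who are breathless at baseline tend to be breathless later, so that hypothesis can be rejected when nobody has changed.

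The plan does not say which table is meant. The first can miss a real improvement. The second can give a very small p-value that says nothing about improvement. Dyspnea is the only before/after comparison in the paragraph that is given an unpaired test, and nothing elsewhere supplies a paired one or describes independent groups to which Fisher's test could apply.

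**Working it through.** **Inputs from the documents.** One arm; 27 patients required and up to 40 enrolled; two-sided 0.05; for mPAP, a difference of 4 mmHg, SD 5.5 and power 0.95. **Assumed, because the documents give nothing:** the dyspnea scale, the effect, and the within-patient correlation.

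**1. The plan's own figure.** A paired t-test with difference 4 and SD 5.5, by the noncentral t distribution, has power 94.5% at n = 26 and 95.3% at n = 27, so 27 is reproduced. Allowing 30% attrition, 27/(1 − 0.30) = 38.6, or 39, consistent with up to 40. This calculation does not involve dyspnea.

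**2. Time-by-score example (assumed counts).** Of 27 patients, 20 are breathless before and 14 after; six improve and none worsen.
- Fisher on [20, 7; 14, 13]: p = 0.158.
- Exact McNemar on six changes, all in one direction: p = 2 × 0.5^6 = 0.031.

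**3. Cross-table example (assumed counts).** Nobody changes: 14 are breathless at both visits and 13 at neither. Fisher on [14, 0; 0, 13] gives p = 1/C(27,14) = 1/20,058,300, about 5 × 10⁻⁸. There are no changes, so McNemar gives p = 1.

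**4. Rejection rate when nothing changes, n = 27.**
- Time-by-score, 60% breathless at both visits, latent correlation 0.3 / 0.5 / 0.7: Fisher 1.3 / 0.7 / 0.2%; exact McNemar 2.3 / 2.0 / 1.5%. Both are below 5%.
- Five-level score, same correlations: Fisher on the 2 × 5 table 3.4 / 2.1 / 1.6%; exact signed-rank 4.1 / 3.9 / 2.9%.
- Cross-table, 50% breathless at both visits, correlation phi of 0.3 / 0.5 / 0.7: Fisher rejects 25 / 67 / 96% of the time.

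**5. Power with a dichotomised score, Fisher (time-by-score) v exact McNemar.** Paired outcomes come from a bivariate normal cut at the stated proportions, so the correlation is that of the latent variable, not phi. Rejection probabilities are summed exactly over all tables.

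| n, change | corr. 0 | 0.3 | 0.5 | 0.7 | 0.8 |
|---|---|---|---|---|---|
| 27, 60% to 35% | 33 v 34% | 31 v 40% | 30 v 46% | 28 v 55% | 26 v 60% |
| 40, 60% to 35% | 55 v 52% | 55 v 61% | 56 v 69% | 56 v 79% | 56 v 86% |
| 40, 70% to 35% | 86 v 83% | 88 v 91% | 90 v 95% | 92 v 98% | 93 v 99% |

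Relative loss is 1 − Fisher/McNemar. For correlations of 0.3 and above it runs from 1 − 88.1/90.7, about 3%, to 1 − 26.2/60.3, about 57%.

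**6. Power with a five-level score, 2 × 5 Fisher v exact signed-rank.** Bivariate normal pairs cut at −1.2, −0.3, 0.6 and 1.4; simulation with 4,000 replicates per cell at n = 27 and 2,000 at n = 40.

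| n, shift | corr. 0.3 | 0.5 | 0.7 | 0.8 |
|---|---|---|---|---|
| 27, 0.5 SD | 20 v 48% | 17 v 58% | 13 v 75% | 10 v 86% |
| 27, 0.75 SD | 48 v 81% | 47 v 91% | 46 v 98% | 44 v >99% |
| 40, 0.5 SD | 32 v 66% | 28 v 78% | 22 v 92% | 20 v 98% |
| 40, 0.75 SD | 73 v 95% | 73 v 99% | 74 v >99% | 74 v >99% |

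The largest relative loss is 1 − 10/86, about 88%. It combines ignored pairing with ignored ordering.

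**The case against.** - **A conservative test still controls false positives.** This stands for the time-by-score table with positive correlation: a significant result there would be credible, and the fault is inefficiency. It is not a general guarantee; with phi = −0.3 and n = 40 (50% breathless at both visits) the rejection rate is 6.2%, though negative correlation is unlikely for repeated dyspnea scores. The plan's wording also fits this table better than the cross-table, so the example with p near 5 × 10⁻⁸ shows the less likely reading.
- **The largest losses are not all due to pairing.** This stands. At n = 27, a 0.5 SD shift and correlation 0.3, an unpaired but ordered rank-sum test has about 38% power, between 20% for Fisher and 48% for signed-rank. About 18 of the 28 points therefore come from ignored ordering and 10 from ignored pairing. At correlation 0.8, rank-sum has about 33 to 34%, between 10% and 86%, so pairing accounts for most of that gap. The dichotomised figures isolate pairing.
- **There need be no loss at all.** At zero correlation and n = 40, Fisher slightly outperforms exact McNemar (55% v 52% and 86% v 83%). The 3% lower end therefore holds only for correlations of at least 0.3 among the cases examined.
- **Signed-rank is a preference while the scale is unknown.** Partly stands. A sign test, a marginal homogeneity test or McNemar could suit a coarse scale, and the instrument may be named on a data collection form that is not in the documents. The need for a paired test does not depend on this.
- **This is an open-label pilot and dyspnea is not primary.** True, and it limits the seriousness. But the plan applies the same significance threshold to all analyses, and dyspnea is in the hypothesis.

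**Conclusion.** The concern holds. The plan states an explicit rule, so this is not merely missing detail, and the rule does not fit paired data. On the time-by-score reading the consequence is lost power without inflated false positives, given positive correlation. For a dichotomised score with latent correlation of 0.3 to 0.8, the relative loss ranged from about 3% to about 57% in the cases examined. For a five-level score it reached about 88%, part of which reflects ignored ordering. On the cross-table reading the p-value does not address change. Every size rests on an assumed scale, effect and correlation; the mismatch between test and design does not. The mPAP and PCWP analyses and the sample size of 27 are untouched. This should be fixed, but it does not threaten the primary result.

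**What to change.** Replace the dyspnea sentence in Statistical Methods with, for example: *Change in Dyspnea Index from Visit 1 to Visit 4 will be tested with the Wilcoxon signed-rank test on the full score, two-sided 0.05.* An exact version that allows for ties is advisable if the score has few levels. Name the instrument and its score range under Functional Assessments. Use exact McNemar only if a cut-point is fixed in the plan before analysis.

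In the same edit, reconcile the six-month interval in this paragraph with the four-month design and the week-18 final visit. That is a separate inconsistency, and the conclusion above does not depend on it.

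The cost is one sentence plus the name and range of the index. No new data, visits or patients are needed, and the sample size does not change.
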